#### Analysis of secondary outcomes: changes in DLQI value and adherence

Changes in DLQI measures from baseline to weeks 12, 24, 36 and 48 will be compared between the two groups by linear mixed model for longitudinal data. DLQI will be presented in box plots and bar charts.

For separate analyses of the three adherence measures (by filled prescriptions, weight of medication and patient reported adherence, respectively), the adherence rate is dichotomized with a selected cut-off of 80%, with adherence rates above 80% considered adherent (a cut-off typically used when studying adherence in chronic diseases) (8, 42). Dichotomized adherences are compared by using logistic regression.

Statistical analysis will be conducted by an experienced statistician. The statistician will not be blinded to the intervention, as any blinding would be difficult to obtain because the participants in the intervention group are subdivided in three different subgroups (grouped according to the nurse delivering the intervention), while the non-intervention group is kept in one group. However, the analysis will comply with the statistical methods outlined in the study protocol. An interim analysis is not planned.

Obtaining LS-PGA and DLQI five times during the study gives extra strength to the analysis, so a smaller difference can be detected, if this is stable over time.

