## **Additional consent provisions for the collection and use of participant data and biological specimens**

The informed consent grants researchers the right to obtain data for research use from the participants medical chart and to link study data to central health registers (for use of medication and other health services) over a two-year period prior to inclusion in the trial and during the trial period.

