## **Economic evaluation**

To assess the effectiveness of the intervention a cost-effectiveness/utility analysis will be performed. The effect measures are Quality adjusted life years (QALY), DLQI and LS-PGA. EQ-5D values (based on danish societal weights) (43) will be used to calculate QALYs (44). The intervention has numerous potential short-term economic benefits within the study period, primarily a reduction of the need for prescribing narrow-band ultraviolet B (UVB) treatment, biologic treatment, systemic antipsoriatic drugs and laboratory analyses used to monitor the use of drugs. Furthermore, the intervention may reduce patients' need for consulting the general practitioner or private dermatologists to obtain a prescription for antipsoriatic treatment. As the intervention may improve patients' well-being, there is likely to be a reduced need for psychological or psychiatric treatment. The intervention is not expected to reduce the incidence of other psoriasis co-morbidities, except for improved well-being. Adverse events will be recorded but not included in the economic evaluation model, as they are assumed to be mild for both groups, thus not incurring relevant costs. Costs and resources will be calculated from a healthcare sector perspective including healthcare system costs. The total healthcare costs (measured in GBP in 2021 prices) for participants will be obtained to compare costs for the intervention group and non-intervention. Cost data for the economic evaluation will be compiled by i) registration at each outpatient visit during the trial period of the time spent by the nurse delivering dermatology support to patients in the intervention group (study personnel will receive a fixed payment per work hour), ii) registration of cost for drugs delivered free-of-charge (by searching the patient medical charts, estimating drugs linked to a unique pharmaceutical item number (45), and iii) extraction of data from the Danish Health registries to compile total healthcare costs, linked to participants' personal identification number, in a two-year period prior to inclusion in the study and during the study period (48 weeks). Data from the Danish Health registries contain real-life

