### **Cost-effectiveness analyses**

The analysis of resource use and costs will be conducted on individual patients' aggregated cost measures during the observation period (48 weeks) from the inclusion date for each individual patient. Regression analyses will be used to estimate incremental cost and QALYs. Because costs are normally right-skewed and QALY left-skewed, generalized linear models are considered. As the intervention and non-intervention might have different resource use at baseline, an adjustment is made for baseline costs (cost of the previous two years). QALYs are adjusted for baseline utility values (50). If appropriate, an adjustment for baseline covariates in the regression analysis of QALY will also be applied. Baseline covariates (self-reported) will be age, gender, marital status, education, psoriasis-age, smoking-status, labour market participation, income, and absenteeism. Models are estimated with and without adjustment for covariates. Missing effect data will be evaluated to assess the occurrence of specific missing data patterns and, if necessary, Multiple Imputation will be used.

The total costs from baseline to 48 weeks after baseline (end of trial) is compared between the two groups and divided by the difference in gain in effect, resulting in an incremental cost-effectiveness ratio (ICER). The ICER is measured as the total cost per QALY gain from baseline to the end of the trial. For this trial, the ICER is a summary measure representing the economic value of the intervention compared to the standard care procedure. A positive ICER reflects the additional costs per one additional unit of the measure of effect. A negative ICER reflects that one of the treatment strategies is dominant. Similarly, an ICER will be computed using DLQI and LS-PGA effect measures. Dominance in the results exists if one strategy is found to be both

cheaper and more effective than the other. The clinical relevance of the analysis will be improved if the ICER reflects what is considered a minimal clinically important difference (MCID) in the DLQI and LS-PGA (that is, at least a two-point difference in the DLQI (37) as well as the LS-PGA (36)). Results will be bootstrapped to obtain confidence limits around the estimate (51, 52). Furthermore, conventional methods to examine the sensitivity of the cost-effectiveness analysis, such as cost-effectiveness acceptability curves (CEAC), will be applied. All analyses will be performed using STATA 16.

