A strength of the study is that participants are blinded to one of the facts, namely that a main purpose of the study is to investigate adherence, since the awareness of being in an adherence-improving trial could in itself influence adherence. The study design is based on systematic literature searches and use of a participatory study design, where the opinions of psoriasis patients and dermatology nurses have been considered. The study aims to provide effective, long-term follow-up and to use a clinically relevant primary endpoint (severity of disease), to collect and compare different adherence measures as well as be relevant for potential future implementation of the study (economic analysis). Patient-reported outcomes (DLQI and EQ-5D) as well as the physician-obtained outcome (LS-PGA) are obtained, which is an advantage of the study since patients' perception of severity of disease and physicians' objective measures do not always correlate (56). To reduce the impact of participants' awareness of being in an adherence-study, a measure of participants' estimated adherence is not obtained at baseline (as would have been necessary if, for example, the validated adherence-measure Morisky Medication Adherence Scale 4-item (MMAS-4) was applied at the baseline study visit and at week 48 (57)).

If the intervention is significantly superior compared to standard patient support, there is potential for implementing the patient-support intervention in the dermatology clinic. Results from the study may also be applied to other chronic dermatological diseases. At the very least, the study may be used methodically as a model for research projects investigating other chronic diseases.

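### The adherence models name no pre-randomisation covariate, although prescription-register data for the two years before inclusion are already planned; the comparison is valid but gives up some precision

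*Combined protocol and SAP*

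**What the plan says.** *Analysis of secondary outcomes: changes in DLQI value and adherence* treats filled prescriptions, weight of medication and patient-reported adherence separately. For each, "the adherence rate is dichotomized with a selected cut-off of 80"%, and "Dichotomized adherences are compared by using logistic regression". No covariate is named.

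The *Discussion* states that "a measure of participants' estimated adherence is not obtained at baseline". The reason given is "To reduce the impact of participants' awareness of being in an adherence-study", and the example is a validated questionnaire given at the baseline visit.

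Elsewhere the plan provides for passive data covering the same behaviour before the trial:

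- *Additional consent provisions* allows linkage to "central health registers (for use of medication and other health services) over a two-year period prior to inclusion in the trial".
- *Economic evaluation* plans register data "linked to participants' personal identification number, in a two-year period prior to inclusion in the study and during the study period (48 weeks"), and names the Danish National Prescription Registry as one source.
- *Data that is considered to be source data* has previous topical treatment over the same two years recorded in REDCap.
- *Information obtained and provided throughout the study* places the register extraction after week 48.

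The pre-trial window is used for adjustment in one place only. In *Cost-effectiveness analyses*, "an adjustment is made for baseline costs (cost of the previous two years").

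**The concern.** LS-PGA and DLQI are analysed as change from baseline, costs are adjusted for prior costs, and QALYs for baseline utility. Adherence alone enters its comparison with no pre-randomisation information.

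Prior use is likely to vary. *Study setting* admits both existing clinic patients and new referrals, and *Sequence generation* describes block randomisation with no stratification. Long-term adherence is the third item under *Objectives*, and the *Discussion* concedes that secondary differences may be hard to detect at this sample size. A prognostic covariate that needs no patient contact would recover some precision.

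Timing matters too. The statistician is not blinded and the register data arrive after week 48. A covariate chosen at that stage would carry little weight, so it has to be written down beforehand.

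**Working it through.** **Does the stated reason exclude register data?** No. The reason is participants' awareness. A register extract made after week 48 involves no contact and cannot change behaviour during the trial.

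**Is the variable within reach?** Largely. Consent covers medication use in the two prior years. Primary adherence is defined by collection of a topical drug within an ATC class and taken from the same registry, so drug-level fills are needed for the trial period in any case. For the pre-trial period, however, *Economic evaluation* describes the prescription data as costs. The drug-level specification therefore has to be extended to that window.

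**Inputs for the size of the gain**

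- Sample size 115, 1:1 (*Sample size*): 115/2 = 57.5, taken as 57 per arm.
- Two-sided 5% test. The section prints a significance level of 95%, read here as 5%.
- Adherent: 40% versus 60%. Assumed; the plan states no adherence rates and no power for these outcomes.
- Latent correlation between covariate and outcome: 0 to 0.7. Assumed; the documents give no value.

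The plan's 115 refers to LS-PGA. It cannot be rebuilt because the mean and SD are not given, and there is no stated adherence figure to reproduce.

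**Unadjusted power by formula**

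- SE under the null: √(2 × 0.5 × 0.5/57) = 0.0937
- SE under the alternative: √((0.4 × 0.6 + 0.6 × 0.4)/57) = 0.0918
- Power: Φ((0.20 − 1.96 × 0.0937)/0.0918) = Φ(0.18) ≈ 57%

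**Adjusted power by simulation.** A standard normal covariate x and a latent adherence score ρx + √(1 − ρ²)e were cut to give 40% and 60% adherent. Logistic regression was fitted with and without x, in 4,000 to 10,000 runs per setting (Monte Carlo standard error about 0.5 to 0.8 points).

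| Latent correlation | Unadjusted | Adjusted |
|---|---|---|
| 0 | 57–58% | 57–58% |
| 0.3 | 56–58% | about 60% (58–60%) |
| 0.5 | 56–57% | 63–64% |
| 0.6 | 57–58% | 68–69% |
| 0.7 | 57% | 73% |

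- **Fewer patients.** With 46 per arm (115 × 0.8/2, a 20% loss assumed), unadjusted power is about 48%. Adjusted power is about 52%, 55% and 64% at correlations 0.3, 0.5 and 0.7.
- **Incomplete history.** With a usable history in only 60% of patients (assumed), 57 per arm and correlation 0.5, power rises from about 58% to 61%.
- **Type I error.** With 50% adherent in both arms and correlation 0.5, it was 4.5% to 5.0% adjusted and 5.2% to 5.4% unadjusted.
- **Chance imbalance.** The difference between arms in a standardised baseline covariate has SD √(2/n): 0.19 with 57 per arm, 0.21 with 46.

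**The case against.** The strongest reply is that nothing is wrong. Randomisation makes the unadjusted comparison valid, and its confidence interval already allows for chance imbalance. The plan also collects previous medicine use to check that the groups are comparable. All of this stands. A reader might infer that leaving out baseline adherence biases the adherence results; the documents do not support that. The cost is precision only.

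A second reply is that past dispensing is a proxy. Amount dispensed also reflects disease extent and prescribing. Weight-based adherence is a ratio to expected use based on body surface area, primary adherence depends on prescriptions issued, and the questionnaire concerns days with a rash. New referrals and patients on stable systemic drugs may have little topical history, and drugs supplied free of charge are found through charts, separately from the register extract. This also stands. It limits the benefit without removing it, since a covariate need only be prognostic and fixed before randomisation.

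A third reply concerns size. A reader might apply the rule for continuous outcomes: residual variance falls to 1 − r², which is 0.91 at r = 0.3 and 0.64 at r = 0.6. That would equal 1/0.91 = 1.10 to 1/0.64 = 1.56 times the patients, and would raise 80% power to about 84% to 94%. The rule belongs to linear regression. For the planned logistic model, starting from 80% power (46 per arm, 36% versus 65% adherent, assumed), simulation gives about 82% to 84% at 0.3 and 89% at 0.6. Nor do the documents suggest 80% power for adherence.

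Finally, adjustment has side effects. The odds ratio becomes conditional on the covariate, and if nearly all patients collect their drug, a model with a covariate may be unstable. Both points stand and shape the fix.

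**Conclusion.** The point holds as a cheap improvement to secondary analyses, not as an error that invalidates them. The awareness argument does not explain leaving out the register data, and no other reason is given.

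Under 40% versus 60% adherent and 57 per arm, one covariate adds about 2 to 3 points of power at a latent correlation of 0.3, 6 to 8 at 0.5, 10 to 12 at 0.6, and nothing at zero. Even so, power stays below 80% across the range examined. The adherence rates and the correlation are assumptions, and a thin history in part of the sample would shrink the gain. The register data should be described as planned and consented, not as already in hand.

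**What to change.** In *Analysis of secondary outcomes*, pre-specify the following before any register data are seen:

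1. For weight-based and patient-reported adherence, include one covariate: topical corticosteroid or calcipotriol dispensing in the two years before inclusion. A single term such as log(1 + amount dispensed) sets patients with no history to zero.
2. For primary adherence, use the covariate only if the number of non-adherent patients, counted over both arms together, reaches a minimum stated in advance. Otherwise keep the unadjusted comparison.
3. Report the unadjusted result alongside, or a standardised risk difference, and say which is the main estimate, because the adjusted odds ratio is conditional.

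In *Economic evaluation*, state that the pre-trial prescription extract is at ATC and fill level, as *Primary adherence* already requires for the trial period. In *Data management*, extend the stated purpose of the transfer to the secure server from the economic analysis to the adherence models. If the drug-level extract cannot be had, the topical treatment history in REDCap is a coarser fallback.

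The cost is one derived variable, a few lines of text and a clarified extract specification, with no patient contact. The main drawback is that the proxy may prove weak in newly referred patients or those on stable systemic drugs.

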### **Concealment mechanism**

The randomization code will be stored by a data manager. Furthermore, participants are informed that the purpose of the study is to investigate the effect of the prescribed topical drugs.

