## Statistical methods

### Statistical methods for primary and secondary outcomes

#### Analysis of the primary outcome: changes in LS-PGA

Changes in LS-PGA measures from baseline to week 12 and from baseline to weeks 24, 36 and 48 will be compared between the two groups by linear mixed model for longitudinal data. LS-PGA will be presented in box plots and bar charts.

Two sensitivity analyses on LS-PGA data will be carried out in which all study participants will be included: i) a complete case analysis, and ii) an imputed analysis (after 100 times multiple imputations by multivariate normal regression on LS-PGA data) with all covariates.

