## **Analysis methods to handle protocol non-adherence and any statistical methods to handle missing data**

Missing data on the primary outcome will be evaluated to assess the occurrence of specific missing data patterns, and if necessary, missing data will be handled by using multiple imputation. Missing effectiveness values are imputed at missing time points using values from available time points. Furthermore, missing data will not be imputed for PRO outcomes or adherence measures.

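### The reason given for an unblinded statistician covers only the nurse and telephone interaction analyses; the LS-PGA, DLQI and adherence comparisons could be run on arm-masked data

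*Combined protocol and SAP*

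**What the plan says.** All references are to the combined protocol and SAP.

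Under *Analysis of secondary outcomes*, the plan says: "The statistician will not be blinded to the intervention, as any blinding would be difficult to obtain". The reason given is that "participants in the intervention group are subdivided in three different subgroups (grouped according to the nurse delivering the intervention", whereas controls are kept as one group. The same paragraph commits the analysis to the methods set out in the protocol.

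The planned clinical comparisons are:
- LS-PGA changes "will be compared between the two groups by linear mixed model for longitudinal data" (*Analysis of the primary outcome*).
- "Changes in DLQI measures from baseline to weeks 12, 24, 36 and 48 will be compared between the two groups", also by linear mixed model.
- "Dichotomized adherences are compared by using logistic regression", after a cut at 80%.

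*Methods for additional analyses* adds interaction terms for nurse and for the share of contacts made by telephone. On missing primary-outcome data, the plan says that "if necessary, missing data will be handled by using multiple imputation". On custody of the allocation, *Concealment mechanism* says: "The randomization code will be stored by a data manager". *Who will be blinded* names only the data assessor. The *Discussion* lists the unblinded analyst among the sources of bias.

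**The concern.** The justification is specific: the nurse grouping gives the arm away. That is true of any dataset that carries nurse identity. The question is whether the main comparisons need that variable. If they do not, the stated obstacle disappears for them, and a safeguard has been given up for a reason that belongs to a later, additional analysis.

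At stake are decisions the plan leaves to the analyst. With the arms known, such decisions can be influenced by the result they produce, even unintentionally. Participants, investigator and study nurses are also unblinded, so masking at the analysis stage is worth having where it is feasible.

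**Working it through.** The point contains no figure to reproduce. The check has three steps: which variables each analysis needs, whether the remaining data would reveal the arm, and which choices are still open.

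**Step 1. Does the analysis need nurse identity?**

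| Analysis | Method stated | Nurse term named? | Two-level arm code enough? |
|---|---|---|---|
| LS-PGA (primary) | Linear mixed model, two groups | No | Yes |
| DLQI | Linear mixed model, two groups | No | Yes |
| Three adherence measures | Logistic regression | No | Yes |
| Nurse and telephone interactions | Interaction terms in regression | Yes | No |
| Economic evaluation | Regression on costs and QALYs | No, but nurse time is a cost item in the intervention arm | No; the cost data reveal the arm |

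The stated reason therefore applies to the fourth row. The fifth row cannot readily be masked either, for a different reason.

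**Step 2. Would an A/B-coded dataset still reveal the arm?** LS-PGA and DLQI are collected in both arms at the same five visits (baseline and weeks 12, 24, 36 and 48), so the outcome schedule does not separate the arms. Allocation is 1:1, so group size should not either. Three kinds of field would give the arm away:
- nurse identity;
- records of the nine extra nurse contacts and their mode, which exist only in the intervention arm;
- consultation time, which trial staff record (*Data that is considered to be source data*) and which is planned to differ between arms.

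All three must be left out of the masked export. None is needed for the first three rows of the table.

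**Step 3. Which choices are still open?**
1. *Whether to impute LS-PGA.* The missing-data section makes this conditional on what is found. The primary-outcome section, by contrast, fixes two sensitivity analyses: complete case, and multiple imputation repeated 100 times. The two sections sit awkwardly together.
2. *Covariates of the imputed analysis.* All covariates are to be used, but none is listed for that analysis. This affects a sensitivity analysis, not the primary estimate.
3. *Primary time point or contrast.* Changes to weeks 12, 24, 36 and 48 are all compared, and none is named as the primary result.
4. *Self-reported adherence.* The scale has grades 0–25, 26–50, 51–75 and 76–100% of days. The 80% cut falls inside the top grade, so no grouping of grades matches it. Counting only grade 4 as adherent, for example, puts the working threshold at 76%.

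The first three concern LS-PGA and the fourth a secondary outcome. Imputation is ruled out for patient-reported outcomes and adherence, so choices 1 and 2 do not extend to those.

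**The case against.** The strongest reply is that the lack of masking is disclosed, explained and partly mitigated. LS-PGA and package weights are measured by an assessor blinded to allocation, who sees the patient first while the patient is told not to talk beyond a greeting. The analysis is tied to the protocol's methods, the *Discussion* declares the limitation, and no biased decision has been shown. The open choices are gaps in prespecification, and masking alone would not fill them. Much of this stands, and it limits the point to a modest one. It does not rescue the stated reason, and a commitment to the protocol's methods cannot settle choices that those methods leave open.

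A second reply is that the main models might be meant to allow for nurse effects, a worry the *Discussion* raises. Three clusters in one arm would then reveal it, and the reason would apply. No such term is specified for those models.

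A third is that the cost is assumed. The documents say that a data manager stores the code but describe no export role, and *Availability of data and materials* gives certain study members access to the full data. Whether the statistician is among them is not shown. This stands: access must be restricted as well as the data recoded.

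Two stronger readings are tempting. A reader might infer that analyst masking is nearly the only protection left for the primary result; the blinded assessor contradicts that. A reader might also infer that covariate adjustment of the LS-PGA model is left to the analyst's judgement. The conditional adjustment in *Cost-effectiveness analyses* belongs to the QALY regression, where results are produced both with and without covariates.

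**Conclusion.** The point holds in limited form. The reason given for leaving the statistician unblinded covers the nurse and telephone interactions, not the LS-PGA, DLQI and adherence comparisons as written. The exposure is four open analytic choices, one of which touches only a sensitivity analysis and one only a secondary outcome. Their effect on the results cannot be quantified from the documents. This is a cheap improvement to a declared design choice; nothing here shows that the primary result would be biased.

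The conclusion assumes that the main models contain no nurse effect, as the text now stands, and that the data manager can produce a recoded export. The low cost is a judgement, since the documents give no figure.

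**What to change.** Replace the sentence on the statistician's blinding with a two-stage rule:

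1. The data manager supplies the statistician with a dataset in which the arms are coded A and B and which omits nurse identity, contact-mode and consultation-time fields. The statistician has no access to the unmasked full data until lock.
2. Missing-data decisions and the LS-PGA, DLQI and adherence comparisons are completed and locked on that dataset. The arms are then unmasked and the nurse and telephone variables released for the interaction analyses.

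State that the economic evaluation is outside this rule because nurse-time costs identify the arm. If a nurse effect is intended in the main models, say so; the present justification would then apply to them.

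Masking does not specify the open choices. The same revision should reconcile the two statements on imputation, list the covariates, name the primary time point or contrast, and state how the four grades map to the 80% cut.

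The cost is one recoded export, an access restriction until lock, and subgroup analyses run as a second step. Masking may be imperfect if the arms differ visibly in the data. No visit, procedure, treatment or sample size changes.
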